### 1.3 Schedule of Activities

The SoA for the study is presented in Table 1.

**Table 1 Schedule of Activities**

Assessments	Screening (Day -3 to Day -1 n )	Daily until hospital discharge	Day 14 or discharge f	Day 20 (±3 days) after first dose	Day 28 (±3 days) after first dose	Safety follow-up 28 (±3) days after last dose of acalabrutinib g,h	Details in CSP section
Informed consent	X						A 3
Demography	X						5.4
Determine eligibility	X						5.1, 5.2
Medical history and COVID-19 epidemiology	X						8.2.1
Physical examination (symptom driven, including lung auscultation), height, weight	X						8.2.2
Chest imaging	X r	As clinically indicated					8.2.2
Electrocardiogram	X n	As clinically indicated	X				8.2.4
Echocardiogram	As clinically indicated	As clinically indicated					8.2.4
Pulmonary assessments (oxygen usage, ventilator parameters)	X	X	X		X		8.1.1
Clinical assessments (mSOFA)	X	Day 3, 5, 7, and 10	X				8.1.2.1
9-point category ordinal scale	X	X	X		X		8.1.1.2
Vital signs (blood pressure, respiratory rate, pulse oximetry, heart rate, and body temperature)	X s	X		X	X		8.2.3
Arterial blood gases p	X	X	X		X		8.1.1.1, 8.2.3
Local laboratory assessments:							
Urine or serum pregnancy test (for WOCBP only)	X			X		X	8.2.5.1
Hematology b	X	X	X	X	X	X	8.2.5.1
Serum or plasma chemistry c	X	X	X	X	X	X	8.2.5.1
Hepatitis B and C testing d	X	As clinically indicated				As clinically indicated	8.2.5.1, 8.2.5.1.1

**Table 1 Schedule of Activities**

Assessments	Screening (Day -3 to Day -1 n )	Daily until hospital discharge	Day 14 or discharge f	Day 20 (±3 days) after first dose	Day 28 (±3 days) after first dose	Safety follow-up 28 (±3) days after last dose of acalabrutinib g,h	Details in CSP section
Fibrinogen o	X	qod					8.2.5.1
PT, aPTT, and INR o	X	qod					8.2.5.1
D-dimer o	X	qod	X		X		8.2.5.1
CRP	X	X	X		X		8.2.5.1
Cardiac troponin I o	X	qod					8.2.5.1
SARS-CoV-2 RT-PCR virus testing for eligibility e	X						8.2.5.1
Central laboratory assessments: q							
Acalabrutinib PK i,k		Pre-dose and 0.5, 1, 2, 4, 6, and 12 hours j post-dose (on PK Visit 1, PK Visit 2, and PK Visit 3 j )					4.1, 8.5.1
Acalabrutinib administration		bid (q12h) × 14 days (maximum)					6.1.2
Adverse events	X	X	X	X	X	X h	8.3
Concomitant medications	X	X	X	X	X	X h	NA
Survival status			X	X	X	X h	NA

**Table 1 Schedule of Activities**

Assessments	Screening (Day -3 to Day -1 n )	Daily until hospital discharge	Day 14 or discharge f	Day 20 (±3 days) after first dose	Day 28 (±3 days) after first dose	Safety follow-up 28 (±3) days after last dose of acalabrutinib g,h	Details in CSP section
-------------	--	--------------------------------	----------------------------------	-----------------------------------	-----------------------------------	---	------------------------

- a Pre-dose.
- b Hematology: complete blood count with differential includes, but not limited to white blood cell count, hemoglobin, platelet count, absolute neutrophil count or percentage, red blood cell count, absolute monocyte count or percentage, and absolute lymphocyte count or percentage.
- c Serum or plasma chemistry: albumin, alkaline phosphatase, alanine aminotransferase, aspartate aminotransferase, bicarbonate, blood urea nitrogen, calcium, chloride, creatinine, glucose, lactate dehydrogenase, magnesium, phosphate/phosphorus, potassium, sodium, total bilirubin (direct and indirect bilirubin, if available), total protein, and uric acid.
- d Hepatitis serology must include, at a minimum, HBsAg, anti-HBc, and HCV antibody. If additional hepatitis serology is collected per institutional guidelines, it should be recorded in the database. Participants can be started on acalabrutinib **after** blood samples for all HBV and HCV serology tests and for both HBV and HCV PCR tests have been collected, even if the results are not yet available at the time of first dose administration. Follow the hepatitis serology guidelines described in Section 8.2.5.1.1.
- e Hospitalized with coronavirus (SARS-CoV-2) infection, confirmed by PCR test or other commercial or public health assay in any specimen, as documented by either of the following: 1) PCR positive in sample collected < 72 hours prior to first dose; OR 2) PCR positive in sample collected ≥ 72 hours prior to first dose (but no more than 14 days prior to first dose), documented inability to obtain a repeat sample (eg, due to lack of testing supplies, limited testing capacity, results taking > 24 hours, etc), AND progressive disease suggestive of ongoing SARS-CoV-2 infection.
- f If a participant is discharged prior to Day 14, he/she needs to visit the site for an assessment 2 to 4 days after discharge. Assessments should match those for Day 14.
- g All participants should have follow-up assessments for safety 28 (± 3) days after the last dose of acalabrutinib.
- h Telemedicine is recommended for capturing adverse events, concomitant medications, and survival status. Safety laboratory tests can be done at the hospital or a local laboratory provided the results are ultimately captured in the clinical database for the study.
- i **PK Visit 1:** PK sampling will occur on Day 1 (ie, first dosing day for acalabrutinib suspension).  
**PK Visit 2:** PK sampling can occur as early as Day 2 (if participant has been on a PPI for ≥ 4 consecutive days prior to receiving the third acalabrutinib dose), and up to Day 4 (if participant initiated PPI treatment 24 hours prior to receiving the first dose of acalabrutinib on Day 1). See Section 4.1 for additional details.  
**PK Visit 3:** PK sampling will occur 3 days after PK Visit 2, OR on the last day the participant receives acalabrutinib treatment, whichever comes first.
- j PK sampling will occur at pre-dose and 0.5 (± 5 min), 1 (± 5 min), 2 (± 15 min), 4 (± 15 min), 6 (± 15 min), and 12 (± 60 min) hours post-dose, [REDACTED] sampling will occur at pre-dose and 4 (± 15 min) and 12 (± 60 min) hours post-dose. The 12-hour post-dose PK [REDACTED] samples will be collected immediately prior to administration of the subsequent acalabrutinib dose.
- k The timing of PK [REDACTED] sample collections should be aligned as closely as possible and will be prioritized over other blood samples being collected simultaneously, except in the case of an adverse event for which relevant assessment/blood sample collection will be prioritized.
- l [REDACTED]
- m [REDACTED]
- n Screening can be performed within 1 to 3 days prior to dosing, depending on the local requirements for laboratory turnaround times; ECG can be collected at any time during this screening window.
- o Fibrinogen, PT, aPTT, INR, D-dimer, and cardiac troponin I should be performed more frequently if clinically indicated.

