PK Visit 2	Second PK sampling will occur a minimum of 4 days after the start of PPI treatment, irrespective of the timing of NG tube placement and any time after 2 doses of acalabrutinib suspension have been given (ie, PK sampling can begin prior to the third dose, or anytime thereafter)  PK Visit 2 can occur as early as Day 2 (if participant has been on a PPI for $\geq 4$ consecutive days prior to receiving the third acalabrutinib dose), and up to Day 4 (if participant initiated PPI treatment 24 hours prior to receiving the first dose of acalabrutinib on Day 1)	PPI exposure must occur for 4 consecutive days to reach the maximum PPI on-target effect PK sample can commence at any point after the second dose of acalabrutinib suspension to ensure steady-state levels of the active metabolite and maximal [REDACTED] has been reached
PK Visit 3	Third PK sampling will occur 3 days after PK Visit 2, OR on the last day the participant receives acalabrutinib treatment, whichever comes first	Allows an additional opportunity to assess the steady-state PK of acalabrutinib and ACP-5862 PK following delivery of acalabrutinib suspension via NG tube

Safety assessments, including AE reporting, will be performed through 28 ( $\pm 3$ ) days after the last dose of the acalabrutinib suspension.

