**Table 1 Schedule of Activities**

Assessments	Screening (Day -3 to Day -1 n )	Daily until hospital discharge	Day 14 or discharge f	Day 20 (±3 days) after first dose	Day 28 (±3 days) after first dose	Safety follow-up 28 (±3) days after last dose of acalabrutinib g,h	Details in CSP section
-------------	--	-----------------------------------	-------------------------------------	--	--	--	------------------------------

p Arterial blood gases should be collected from participants if the sample is easily accessible and the procedure will not be painful to participants (ie, participant is in ICU or has arterial port). All available data from the arterial blood gases should be entered into the database. If the collection of arterial blood gases is not clinically indicated, the test should not be performed.

q For all central laboratory assessments, sample collection windows of ± 1 day will be allowed for each of Days 4, 7, and 10.

r Per standard of care, chest imaging can be done by chest x-ray or CT scan with contrast, or any other appropriate means to confirm pneumonia prior to or upon hospitalization (within 7 days of enrollment).

s During screening, vital signs should be collected as close as possible to the dosing on Day 1. If more than one value is obtained for vital signs during screening, the value closest to the first dose of study intervention should be used.

anti-HBc = antibody to hepatitis B core antigen; aPTT = activated partial thromboplastin time, bid = twice daily; COVID-19 = coronavirus disease 2019; CRP = C-reactive protein; CSP = Clinical Study Protocol; CT = computed tomography; ECG = electrocardiogram; HBsAg = hepatitis B surface antigen; HBV = hepatitis B virus; HCV = hepatitis C virus; ICU = intensive care unit; INR = international normalized ratio; mSOFA = modified Sequential Organ Failure Assessment; NA = not applicable; [REDACTED] PCR = polymerase chain reaction; [REDACTED] PK = pharmacokinetics; PPI = proton-pump inhibitor; PT = prothrombin time; qod = every other day; q12h = every 12 hours; RT-PCR = reverse transcriptase-polymerase chain reaction; SAE = serious adverse event; SARS-CoV-2 = severe acute respiratory syndrome coronavirus 2; WOCBP = women of childbearing potential.

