### **6.1.2.3 Missed Dosing Windows and Doses**

The bid doses should be scheduled approximately 12 hours apart. It is recommended that acalabrutinib be taken as close to the scheduled time as possible (within  $\pm 1$  hour). However, if the scheduled time is missed, it can be taken up to 3 hours after the scheduled time, with a return to the normal schedule upon the following dose for 14 days (a maximum of 28 doses).

If the 3-hour dosing window is missed, the dose must be skipped on that day. Acalabrutinib may be held for a maximum of 3 consecutive days (6 consecutive doses) from expected dose due to toxicity. If a dose is missed due to an AE or for any other reason, missed doses should be completed so the participant receives a maximum of 28 doses of acalabrutinib, even if this is beyond the 14-day dosing period.

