### 8.2.5.2 Central Laboratory Tests

Samples will be collected as specified in the SoA (Table 1) and sent to a central laboratory for the following laboratory tests:

- Plasma samples for acalabrutinib/ACP-5862 PK

**NOTE:** PK, [REDACTED] are considered Tier 1 and should not be missed. The site must follow the SoA.

Refer to the Laboratory Manual for instructions on processing and shipping. Additional handling information is provided in Appendix C.

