### 9.2 Sample Size Determination

A sample size of 16 evaluable participants with COVID-19 was chosen based on the desire to gain adequate information while exposing as few participants as possible to the study procedures and study intervention. Given the inherent variability in the COVID-19 patient population, broad inclusion and exclusion criteria, and possible variability in treatment duration and PPI usage, approximately 20 participants will be enrolled in the study in order to have at least 16 evaluable participants able to complete PK Visit 2 (allowing for ~25% dropout rate due to disease progression).

**Note:** “Enrolled” means a participant’s, or his/her legally acceptable representative’s, agreement to participate in a clinical study following completion of the informed consent process. Potential participants who are screened for the purpose of determining eligibility for the study but are not randomly assigned/assigned in the study, are considered “screen failures”, unless otherwise specified by the protocol.

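### The timing of PK Visit 2, which decides who is evaluable, is inconsistent at its early end (Figure 1 against the text) and has no clear latest day

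*Protocol*

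**What the plan says.** Section 4.1 makes completion of PK Visit 2 the first of three conditions for being evaluable. Section 9.2 builds enrolment on it: "approximately 20 participants will be enrolled in the study in order to have at least 16 evaluable participants able to complete PK Visit 2".

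The timing of the visit is given in several places.

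- **Synopsis and Table 4.** Two conditions must both hold. At least 4 days must have passed since the PPI was started, and sampling may be "any time after 2 doses of acalabrutinib suspension have been given (ie, PK sampling can begin prior to the third dose, or anytime thereafter". No latest day follows. The same cell then gives a range from Day 2 to Day 4, with each end tied to when the PPI was started.
- **Table 1 footnote i and the note to Figure 1.** These repeat only the range, ending "and up to Day 4 (if participant initiated PPI treatment 24 hours prior to receiving the first dose of acalabrutinib on Day 1". Both refer the reader on, to Section 4.1 and Table 4 respectively.
- **Figure 1, scenario rows.** A PPI start on Day -1 gives Visit 2 on Day 3. Starts on Day -2, Day -3, and Day -4 or earlier all give Day 2.
- **Table 1 footnote q.** "For all central laboratory assessments, sample collection windows of ± 1 day will be allowed for each of Days 4, 7, and 10". Section 8.2.5.2 lists "Plasma samples for acalabrutinib/ACP-5862 PK" among the central tests, and footnote q is attached to the heading above the PK row.

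Three other provisions bear on the late end. Section 6.1.2.3 allows a treatment hold: "Acalabrutinib may be held for a maximum of 3 consecutive days (6 consecutive doses) from expected dose due to toxicity". Sections 4.1 and 6.5.1 allow the PPI to be withdrawn during the study. Section 6.1.2.2 moves participants who can swallow on to capsules.

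**The concern.** Visit 2 exists to sample the suspension at full PPI effect; Table 4 says so in its rationale column. The state of the PPI at sampling is not a detail. Section 2.2.3.4 reports that omeprazole lowered acalabrutinib AUC by 42% and Cmax by 73% with ordinary dosing, and the suspension is meant to overcome this.

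If one site follows Figure 1 and another the text, the first can draw the key profile a day before the stated minimum. If no latest day applies, a participant who has stopped the PPI, or who now swallows capsules, can supply a complete Visit 2 and be counted among the 16. That profile does not answer the question the 16 were enrolled for. Visit 3 is timed from Visit 2, so a shift in one carries into the other.

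**Working it through.** **The plan's own enrolment figure.** Section 9.2 states 16 evaluable, about 20 enrolled, and "allowing for ~25% dropout rate due to disease progression". Adding 25% gives 16 × 1.25 = 20. Dividing by the retained share gives 16 / 0.75 = 21.3, so 22; 20 × 0.75 = 15 expected evaluable. Both are within the tolerance of an approximate 20. The count of 16 rests on no power calculation ("A sample size of 16 evaluable participants with COVID-19 was chosen based on the desire to gain adequate information"), so no power figure depends on the Visit 2 window.

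**Day numbering.** Table 1 labels screening Day -3 to Day -1, and footnote n describes it as 1 to 3 days before dosing. So Day -k is k days before Day 1 and there is no Day 0.

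**Early end.** For a PPI begun on Day -k and a visit on Day v, elapsed days of PPI = k + (v - 1). The calendar count including both ends is one more. The earliest compliant day is the first v of at least 2 with k + (v - 1) of at least 4.

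| PPI start | Visit 2 in Figure 1 | Elapsed days | Calendar days, inclusive | Earliest day on 4 elapsed days |
|---|---|---|---|---|
| Day -1 | Day 3 | 1 + 2 = 3 | 4 | Day 4 |
| Day -2 | Day 2 | 2 + 1 = 3 | 4 | Day 3 |
| Day -3 | Day 2 | 3 + 1 = 4 | 5 | Day 2 |
| Day -4 | Day 2 | 4 + 1 = 5 | 6 | Day 2 |

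The last column runs from Day 2 to Day 4, exactly the range in the text. The text therefore counts elapsed days. Scenarios 1 and 2 fit only if both the start day and the visit day are counted. The protocol does not say which count applies, so a Day 3 profile after a 24-hour PPI lead-in is on time in the figure and early in the note beneath it.

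A Day 0 would reconcile the two: Day -1 to Day 3 and Day -2 to Day 2 would each be 4 elapsed days. But footnote n points the other way.

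**Late end.** Two doses on Day 1 and six held doses on Days 2, 3 and 4 put the third dose on Day 5. That is allowed by the open-ended sentence, and late if Day 4 is read as a ceiling. Read as open-ended, the limit is the end of dosing: 28 doses at 2 a day is Day 14, later if missed doses are made up.

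Nothing in the evaluability conditions of Section 4.1 asks whether the participant is still on a PPI or still dosed by tube at Visit 2. The 4-day condition in Table 4 runs from the start of the PPI, so it remains met after the PPI is stopped. Inclusion criterion 5 asks only that the tube be expected to stay for 3 days after enrolment. For someone enrolled as late as Day 1 that runs to Day 4, the earliest Visit 2 day in the text for a 24-hour PPI lead-in.

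**Footnote q.** On the text's reading, that same participant has Visit 2 on Day 4 and Visit 3 on Day 7, two of the three days footnote q names. Taken literally, minus 1 day gives Day 3, or 1 + 2 = 3 elapsed days, below the minimum.

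**The case against.** A reader might infer three mutually incompatible windows: any time after dose 2, Day 2 to Day 4, and Day 4 plus or minus 1 day. The documents do not support that.

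- The first omits the 4-day PPI condition, which applies jointly with the two doses.
- The second is best read as the span of earliest permissible days. It sits in the same Table 4 cell as the open-ended sentence, and footnote i sends the reader there. It is not a rival rule, although its wording can be taken as a ceiling.
- The third is not shown to be a Visit 2 rule. PK is scheduled by visit, with its own footnotes and minute-level windows, and Day 10 matches no PK visit in Figure 1. Footnotes l and m are blacked out, and the amendment summary mentions a Table 1 swab that is no longer visible. Footnote q probably serves redacted rows. What remains is that its wording covers every central assessment and does not exempt PK.

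A reader might also infer a lower chance of reaching 16. The binomial probability of at least 16 of 20 is 0.630 at 20% loss, 0.415 at 25% and 0.238 at 30%. But no passage says that a Visit 2 after Day 4 is excluded, so an extra 5% or 10% loss from timing would be pure assumption. The 0.415 is simply what the protocol's own dropout of about 25% already gives.

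Finally, the consequence is bounded. The PK Analysis Set in Table 9 needs one dose and one evaluable post-dose data point, and Section 9.4.2 plans no formal PK test. All of this stands. None of it removes the disagreement between Figure 1 and the text, or supplies a latest day.

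**Conclusion.** The point holds in a limited form. At the early end, two of the four Figure 1 scenarios place Visit 2 one day before the text's minimum. This assumes no Day 0, which footnote n implies, and elapsed-day counting, which the text's own Day 4 example implies. At the late end, no latest day is stated unambiguously, and the evaluability conditions do not require the participant to be on suspension and a PPI when sampled. Footnote q is a loose end, not a proven conflict.

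The effect falls on which profiles count towards the 16 and on how comparable the Visit 2 profiles are. It does not touch membership of the PK Analysis Set or any power statement. The number of participants affected cannot be derived from the protocol, and no loss of probability of reaching 16 should be claimed.

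**What to change.** Reconcile the Synopsis table, Table 4, Figure 1 (scenario rows as well as the note) and Table 1 footnotes i and q:

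1. State how the 4 days of PPI are counted, and make the Figure 1 scenario days agree. On elapsed days, Scenarios 1 and 2 change; on inclusive calendar days, the Day 4 example in the text changes.
2. Word the Day 2 to Day 4 range, adjusted to the count chosen, as the earliest possible day by PPI start and not as a ceiling.
3. State that Visit 2 is sampled at the first feasible dose meeting both conditions, and that it counts as evaluable only if taken while the participant is receiving suspension by tube and is on a PPI.
4. State that footnote q does not apply to PK samples, which follow footnotes i and j.

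These are changes to sampling and counting rules only. The provisions on PPI withdrawal, capsules and treatment holds stay as they are. The cost is wording in a handful of places, plus one real downside: a few late Visit 2 profiles would no longer count as evaluable, though they would stay in the PK Analysis Set.

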**Table 1 Schedule of Activities**

Assessments	Screening (Day -3 to Day -1 n )	Daily until hospital discharge	Day 14 or discharge f	Day 20 (±3 days) after first dose	Day 28 (±3 days) after first dose	Safety follow-up 28 (±3) days after last dose of acalabrutinib g,h	Details in CSP section
-------------	--	-----------------------------------	-------------------------------------	--	--	--	------------------------------

p Arterial blood gases should be collected from participants if the sample is easily accessible and the procedure will not be painful to participants (ie, participant is in ICU or has arterial port). All available data from the arterial blood gases should be entered into the database. If the collection of arterial blood gases is not clinically indicated, the test should not be performed.

q For all central laboratory assessments, sample collection windows of ± 1 day will be allowed for each of Days 4, 7, and 10.

r Per standard of care, chest imaging can be done by chest x-ray or CT scan with contrast, or any other appropriate means to confirm pneumonia prior to or upon hospitalization (within 7 days of enrollment).

s During screening, vital signs should be collected as close as possible to the dosing on Day 1. If more than one value is obtained for vital signs during screening, the value closest to the first dose of study intervention should be used.

anti-HBc = antibody to hepatitis B core antigen; aPTT = activated partial thromboplastin time, bid = twice daily; COVID-19 = coronavirus disease 2019; CRP = C-reactive protein; CSP = Clinical Study Protocol; CT = computed tomography; ECG = electrocardiogram; HBsAg = hepatitis B surface antigen; HBV = hepatitis B virus; HCV = hepatitis C virus; ICU = intensive care unit; INR = international normalized ratio; mSOFA = modified Sequential Organ Failure Assessment; NA = not applicable; [REDACTED] PCR = polymerase chain reaction; [REDACTED] PK = pharmacokinetics; PPI = proton-pump inhibitor; PT = prothrombin time; qod = every other day; q12h = every 12 hours; RT-PCR = reverse transcriptase-polymerase chain reaction; SAE = serious adverse event; SARS-CoV-2 = severe acute respiratory syndrome coronavirus 2; WOCBP = women of childbearing potential.

